7.2.3.2. Adverse Events

- **Adverse events**

The number and percentage of patients with Adverse events will be tabulated by SOC and PT.

- Serious adverse events (SAE)

The number and percentage of patients with SAEs will be tabulated by SOC and PT.

- Non-serious adverse events

The number and percentage of patients with non-serious adverse events will be tabulated by SOC and PT.

7.2.3.3. Other endpoints

None

7.2.3.4. Subgroup Analysis

The number and percentage of patients who experienced at least one adverse drug reaction will be tabulated for each factor specified in Section 4.5. The statistical tests stated in Section 7.1 will be performed to evaluate the association between the patient background factors and development of adverse drug reactions.

The number and percentage of patients who experienced adverse drug reactions will be tabulated by SOC and PT for each of the subgroups defined by the following factor:

- Reason for the use of Mycobutin [MAC (therapeutic), MAC (prophylactic), tuberculosis, NTM other than MAC]

Similar analysis will also be performed for serious adverse drug reactions and SAEs.

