#### **3. Survey Period**

- 1) In principle, the drugs for the treatment of HIV infection are designated as orphan drugs, and the reexamination period for each drug is 10 years as a rule (see P. 6).
- 2) The end date of patient registration for the drug use investigation is as mentioned in page 6.
- 3) This survey will enroll patients, who are the continuing patients from clinical trials or clinical trials conducted from a humanitarian point of view (expanded access program in Japan), separately after the concerned drugs are approved. Also, the survey will enroll patients, who are the continuing patients from post-marketing clinical trials, separately after the trials of the concerned drugs are completed.

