#### **4. Procedures**

This survey is a joint survey by companies having drugs for the treatment of HIV infection which are subject to

reexamination (hereinafter referred to as “joint survey participating companies”) and will be outsourced to a contracted company [CMIC-PMS Co., Ltd. (hereinafter referred to as “CRO”).

1) Request for the survey and a contract

- (1) A request and contract for the survey will be, in principle, made between the CRO and a site.
- (2) For sites with which contracts have been concluded, the CRO will inform the joint survey participating companies that the contracts with the sites have been completed.

2) Method for data collection

In this survey, patient registration, input of data on survey items, and data verification will be carried out using the EDC system. The system to be utilized will be ARCS + PMS (hereinafter referred to as “the System”). Security for data transmission will be ensured by authentication of the user’s ID and password assigned to each investigator and in accordance with the latest SSL encrypted communication protocol.

3) Patient registration

- (1) After the user’s ID and password are issued for each investigator upon the conclusion of the contract, the investigator should enter and send required items (medical record or identification number, patient’s initials [as necessary], gender, birth date [age such as age group as necessary], pregnancy status, inpatient/outpatient status, name of the target drug and start date of treatment), for patients who have newly started receiving drug treatment in or after April of each year or patients who are on drug treatment but have not yet been registered in the survey on the patient registration screen of the System. It is unnecessary to additionally register patients because of drug changes.
- (2) The registration numbers of registered patients will be issued by the System.
- (3) The continuing patients will be automatically kept registered based on data of the previous-year case report forms (CRFs).

4) Points to consider for data entry, revision, and review

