1.1. Study Design

As part of the HRD Joint Survey, this study includes HIV patients for whom Mycobutin is prescribed, including those captured in retrospective surveys. As far as possible, this part of the HRD joint Survey seeks to include all patients who receive Mycobutin at participating medical institutions. The indications and dosage and administration for Mycobutin, the survey periods, and the major investigation items are presented below.

- *Indications*

Susceptible strains: Mycobacteria susceptible to Mycobutin

Indications: Tuberculosis, nontuberculous mycobacteriosis including Mycobacterium avium complex (MAC) infection, and prevention of symptoms of disseminated MAC infection in HIV patients.

- *Dosage and Administration*

Tuberculosis:

For adults, an oral dose of rifabutin 150 mg to 300 mg is administered once daily.

For adults with multi-drug resistant tuberculosis, an oral dose of rifabutin 300 mg to 450 mg is administered once daily.

Treatment of nontuberculous mycobacteriosis including MAC infection:

For adults, an oral dose of rifabutin 300 mg is administered once daily.

Prevention of symptoms of disseminated MAC infection in HIV patients:

For adults, an oral dose of rifabutin 300 mg is administered once daily.

- *Survey Periods*

Tuberculosis and nontuberculous mycobacteriosis including MAC infection:

The survey will start on October 7, 2008, and the registration of patients will end at the end of the fiscal year after the 6th year.

Patient registration: October 7, 2008 - March 31, 2015

Prevention of the symptoms of disseminated MAC infection in HIV patients:

The survey will start on October 7, 2008, and the registration of patients will end at the end of the fiscal year after the 8th year.

Patient registration: October 7, 2008 - March 31, 2017

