4. ANALYSIS SETS

4.1. Safety Analysis Set

The safety analysis set consists of the patients who meet the inclusion criteria for this study and are confirmed to have received at least one dose of Mycobutin. However patients who have received treatment with Mycobutin before marketing (those who discontinued or completed their treatment with Mycobutin before the marketing of Mycobutin[®] 150mg Capsules) will be excluded from the safety analysis set.

4.2. (Preventive) Effectiveness Analysis Set

Among the patients in the safety analysis set, those who received Mycobutin for the prevention of MAC infection and underwent an effectiveness evaluation (determination of whether an onset of MAC infection is observed or not) comprise the (preventive) effectiveness analysis set.

4.3. (Therapeutic) Effectiveness Analysis Set

Among the patients in the safety analysis set, those who underwent at least one post-treatment effectiveness evaluation (determination of bacteriological response or clinical efficacy at the end of the observation period) comprise the (therapeutic) effectiveness analysis set.

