- Non-drug concomitant therapies

- **Status of treatment of Mycobutin**

In the safety analysis set, the exposure of patients to Mycobutin will be tabulated with respect to the following status of treatment:

- Duration of treatment * [≤ 1 week, >1 week to ≤ 2 weeks, >2 weeks to ≤ 4 weeks, >4 weeks to ≤ 8 weeks, >8 weeks to ≤ 12 weeks, >12 weeks to ≤ 24 weeks, >24 weeks to ≤ 36 weeks, >36 weeks to ≤ 1 year, >1 year to ≤ 3 years, >3 years to ≤ 6 years, >6 years to ≤ 8 years, >8 years]
- Duration of one prophylactic or therapeutic treatment [≤ 1 week, >1 week to ≤ 2 weeks, >2 weeks to ≤ 4 weeks, >4 weeks to ≤ 8 weeks, >8 weeks to ≤ 12 weeks, >12 weeks to ≤ 24 weeks, >24 weeks to ≤ 36 weeks, >36 weeks to ≤ 1 year, >1 year]
- Maximum daily dose [<150 mg, 150 mg, 300 mg, 450 mg, >450 mg]

- Mean daily dose [<150 mg, 150 mg, >150 mg to <300 mg, 300 mg, >300 mg to <450 mg, 450 mg, >450 mg]
- Continued or discontinued
- Reason of the use of Mycobutin [MAC (therapeutic), MAC (prophylactic), tuberculosis, Nontuberculous Mycobacteriosis (NTM Infections) other than MAC]

The duration of treatment is defined as the period from the first to the last confirmed dose of Mycobutin during this survey, and does not include the period during which Mycobutin is suspended.

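### The percentage of patients with an ADR by total treatment duration does not show how risk depends on duration; footnote that table and add first-ADR rates by time since Mycobutin start

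*SAP*

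**What the plan says.** The safety subgroup analysis in SAP 7.2.3.4 is a count and percentage: "The number and percentage of patients who experienced at least one adverse drug reaction will be tabulated for each factor specified in Section 4.5". Section 4.5 lists duration of treatment (12 bands, from one week or less to more than 8 years), maximum and mean daily dose, and concomitant drugs including SMX/TMP. It places these under other factors, apart from the patient background factors. The sentence in 7.2.3.4 that commits to statistical tests names only the background factors.

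SAP 7.2.2 defines duration: "The duration of treatment is defined as the period from the first to the last confirmed dose of Mycobutin during this survey", and adds that it "does not include the period during which Mycobutin is suspended". Nothing cuts it at the first reaction. Neither document plans person-time or an incidence rate.

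Patients already on treatment can be in the analysis. Protocol 4 registers "patients who are on drug treatment but have not yet been registered in the survey", Protocol 3 separately enrols those "who are the continuing patients from clinical trials or clinical trials conducted from a humanitarian point of view", and SAP 1.1 describes the population as "including those captured in retrospective surveys". SAP 4.1 excludes only earlier users, namely "those who discontinued or completed their treatment with Mycobutin before the marketing of" the product. Registration records "name of the target drug and start date of treatment". The yearly data entry in Protocol 4 covers the administration status of each drug and the adverse events of the survey period.

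For dose and concomitant-drug factors, including the major-item tables in SAP 7.2.3.1, neither document states a window relative to onset.

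**The concern.** A patient's duration row is known only at the end of treatment and is partly decided by the outcome. Two mechanisms act in opposite directions:

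- More time on drug means more opportunity for a reaction, which raises the percentage in long rows even when the hazard is constant.
- A reaction that ends treatment moves the patient to a short row, which raises the percentage there.

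A reader of the final table could take a rising or falling pattern as evidence about long-term or early risk when it is neither. Identifying factors that affect safety is a stated objective (SAP 1.2). Because the definition counts survey doses only, a patient already on Mycobutin at entry is also placed in too short a row.

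Dose and concomitant-drug tables have a related but less certain problem. If they are read as any use during treatment, longer-treated patients have more chance both to be exposed and to react. SMX/TMP was added to the SAP to study an interaction, so this table is likely to be read closely.

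**Working it through.** The documents give no sample size, ADR rate, stopping fraction or drug start times, so there is no planned figure to reproduce. Every input below is an assumption chosen to show the mechanism.

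**Inputs.** Planned duration: median 168 days, lognormal (sigma 1.3) or exponential, capped at 8.48 years (7 October 2008 to 31 March 2017, the preventive registration window in SAP 1.1). Onset: constant hazard of 0.5 per year, or an early pattern (35% susceptible, mean onset 28 days). A reaction stops treatment with probability 0, 0.5 or 1.

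**Step 1, closed form with a constant hazard.**

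- No reaction stops treatment: P(ADR | duration T) = 1 - exp(-0.5 T). At 6 weeks (42/365.25 years) this is 5.6%, at 18 weeks 15.8%, and at 1.7 years 57.3%. The rise comes from time alone.
- Every reaction stops treatment, exponential durations: the hazard of ending treatment for other reasons is ln 2 / (168/365.25) = 1.507 per year. In every row P(ADR) = 0.5 / (0.5 + 1.507) = 24.9%. The two effects cancel exactly.

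**Step 2, simulation on the SAP's own bands.** Percentage with an ADR in the rows 4-8 weeks / 12-24 weeks / 1-3 years:

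| Durations, onset | None stop | Half stop | All stop |
|---|---|---|---|
| Lognormal, constant | 6/15/56 | 15/20/49 | 22/25/41 |
| Exponential, constant | 6/15/53 | 17/20/42 | 25/25/25 |
| Lognormal, early | 27/35/35 | 38/23/21 | 46/7/0 |
| Exponential, early | 26/34/35 | 40/23/21 | 49/7/0 |

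Repeat runs agreed within about 1 point. In the early pattern with no stopping, the percentage rises and then levels off, although the true rate falls from 4.2 per year in week 1 to 0.01 or less after 24 weeks.

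**Step 3, the alternative measure.** Rate in an interval = first ADRs in that interval / ADR-free person-time in that interval, by time since start. With constant hazard it returned 0.49 to 0.51 per year in every interval up to 3 years, for all stopping fractions. With early onset it returned the same falling curve whatever the stopping fraction.

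**Step 4, two ways to get the rate wrong.** These use a different assumed set: hazard 0.30 per year and exponential durations with mean 1 year.

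- Dividing by person-time but still grouping by total duration does not help. If all reactions stop treatment, the rate runs from 23.9 per year (one week or less) to 0.14 (1-3 years).
- Suppose patients already on drug enter on average 1 year after start, with reactions seen only after entry. Counting their person-time from actual start gives 0.193 instead of 0.30; counting from entry restores 0.30.

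**Step 5, an inert concomitant drug classed by any use.** Lognormal durations, later starts exponential with mean 1 year, both onset patterns and all stopping fractions:

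- 50% on it at start and 20% of the rest assigned a later start: risk ratio about 0.9 to 1.1.
- 50% at start and all the rest assigned a later start: about 0.6 to 2.1.
- 30% at start and all the rest assigned a later start: about 0.5 to 2.4.

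With half the patients on the drug at start in both of the first two cases, the distortion depends strongly on how many start it later. No figure is offered for dose.

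**The case against.** SAP 3.1 treats every p-value as descriptive, and 3.2 sets no decision rule. On its wording, 7.2.3.4 commits tests only for background factors, so the duration, dose and concomitant-drug tables may be purely descriptive. The SAP nowhere says that the duration table measures a duration effect. All of this stands and limits the weight of the point. It does not stop a descriptive table from being misread.

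The time-to-onset table in SAP 7.2.3.1 already addresses timing, and the treatment-duration table in 7.2.2 uses the same cut-points up to 1 year. Cumulating the latter gives approximate numbers still on treatment. That is a real mitigation, but those numbers are not ADR-free and do not give person-time. SAP 7.2.3.5 allows extra analyses, but only optionally.

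The exposure window may be set in the joint-survey standard specifications (SAP 9) or in the separate specifications mentioned in SAP 6. Neither was available, so the supportable statement is that the protocol and SAP do not state a window, not that none exists.

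A reader might infer that the registration date supplies the Mycobutin start date. The documents do not support that in general. It is the date for the target drug in a multi-drug survey, and Protocol 4 requires no new registration when drugs change, so it may belong to another drug. The provision for patients already on treatment likewise covers any target drug.

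**Conclusion.** The point holds as a low-severity improvement. The planned percentages by total duration do not show how risk depends on duration. That follows from the definitions alone.

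Size and direction do not follow from the documents. Under the assumptions shown, with no true change in hazard, the contrast between the 4-8 week and 1-3 year rows ranges from none (25% against 25%) to 6% against 56%. With early onset and all reactions stopping treatment, it reverses to 46% against 0%. A reader might infer that the table must exaggerate long-term risk; it can equally hide or reverse a pattern, depending on stopping behaviour.

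For concomitant drugs, a reader might infer either a large distortion or one confined to drugs that nobody takes at the start. Neither is supported: under the assumptions used, the inert-drug risk ratio stays near 1 when few patients start later and spans about 0.6 to 2.1 when many do, even with half on the drug at the start. Which case applies to SMX/TMP is unknown, and the window may already be defined elsewhere.

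**What to change.** **1. Duration.** Keep the planned table, with a footnote that it cannot be read as an effect of duration. Add first-ADR incidence per person-time by time since Mycobutin start, with exact Poisson 95% confidence intervals. Use the time-to-onset intervals of SAP 7.2.3.1, collapsed where sparse (for example up to 4, 4-12, 12-24 and over 24 weeks). End follow-up at the first ADR or the end of the risk period. State how suspensions, repeat treatments and events after the last dose are handled.

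Take the start date from the Mycobutin administration records. Use the registration date only where the registered target drug is Mycobutin. Count person-time only from the date from which that patient's reactions are captured, and confirm whether retrospective capture under SAP 1.1 reaches further back. Show patients with unknown start or capture dates separately.

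**2. Dose and concomitant drugs, including SMX/TMP and the major-item tables.** If the unseen specifications define a window, cite it in Section 4.5. Otherwise use status at treatment start or up to first onset where dates exist. Keep any-use tables with a footnote that timing relative to the reaction is unknown.

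**3. Tests.** Say whether the Section 7.1 tests apply to the other factors.

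**Cost.** SAP wording, moderate programming, and confirmation of start, capture and concomitant-drug dates; Protocol 5 lists concomitant drugs without mentioning dates. Partial dates will need a rule, which SAP 6 defers. Intervals will be sparse. With an assumed 200 patients, 24% of them already on treatment, and a constant 0.5 per year, each of the first two weekly intervals expects about 1.5 ADRs; the four collapsed intervals expect 5.5 to 38.5 each.

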7.2.3.5. Exploratory Analysis

Additional analyses may be performed as necessary. The results of an exploratory analysis will be reported only when they result in an important interpretation.

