2. INTERIM AND FINAL ANALYSES

In this study, interim analyses for periodic safety update report will be performed periodically. At the time of interim analyses, only the analyses of items necessary for periodic safety update report among the statistical analyses specified in this plan will be performed. In addition, the final analysis for the application for reexamination will be performed. At the time of the final analysis, all analyses specified in this plan will be performed.

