3. HYPOTHESIS AND DECISION RULES

3.1. Statistical Hypothesis

Because this study is not a confirmatory investigation, the tests are considered exploratory and a p-value resulting from a test will be considered as a descriptive statistic with no significance level specified, although a post-hoc threshold value may be introduced for a screening purpose.

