3.2. Statistical Decision Rules

Not applicable.

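### The SAP reports additional, unplanned analyses only when their result is judged important, which builds selective reporting into that part of the plan

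*SAP*

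**What the plan says.** Two identical subsections govern unplanned work: SAP 7.2.3.5 for safety and SAP 7.2.4.5 for effectiveness. Each opens with "Additional analyses may be performed as necessary" and continues: "The results of an exploratory analysis will be reported only when they result in an important interpretation". Neither says what makes an interpretation important or who decides. The listings in SAP Section 8 include no log of additional analyses.

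On p-values, SAP 3.1 says that "a p-value resulting from a test will be considered as a descriptive statistic with no significance level specified". The same sentence then leaves room for a cut-off set later: "although a post-hoc threshold value may be introduced for a screening purpose". It gives no value, timing or disclosure rule for such a threshold. SAP 3.2, on decision rules, reads "Not applicable".

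The planned factor analyses are set out elsewhere. SAP 4.5 names the factors and their categories. Under SAP 7.2.3.4, patients with at least one adverse drug reaction "will be tabulated for each factor specified in Section 4.5", and tests "will be performed to evaluate the association between the patient background factors and development of adverse drug reactions". SAP 7.2.4.4 takes the three effectiveness rates through each Section 4.5 factor. SAP Section 2 adds: "At the time of the final analysis, all analyses specified in this plan will be performed".

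**The concern.** The sentence in 7.2.3.5 and 7.2.4.5 is a positive rule that makes reporting depend on the result. An additional analysis that finds nothing, or nothing thought interesting, leaves no trace in the report. A reader who meets one striking exploratory finding cannot tell whether it was the only analysis tried or one of many.

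This matters because finding factors that affect safety and effectiveness is a stated objective (Protocol Section 1, SAP 1.2). SAP 1.2 also uses the results to judge whether a further survey or a post-marketing clinical study is needed, and a null result bears on that judgement as much as a positive one. The results go into the reexamination and into yearly feedback to healthcare professionals. Protocol Section 6 gives transparency as one reason for disclosing them, which fits poorly with reporting that depends on the result.

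**Working it through.** Neither document states a sample size, power, significance level or number of tests, so there is no figure of the plan's own to reproduce. The check is mainly a reading of the sections against each other.

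**1. Which analyses fall under the rule?** Those not specified elsewhere in the SAP. Setting the sections side by side gives three concrete kinds:

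- *Major investigation items.* SAP 1.2 names hematologic disorders and uveitis. SAP 7.2.3.1 tabulates them overall, by outcome, and by specified concomitant drugs and their dose. SAP 7.2.3.4 applies the Section 4.5 factors to patients with any adverse drug reaction, with similar analysis for serious adverse drug reactions and serious adverse events. It adds a tabulation by organ class and term only by reason for use. Uveitis against CD4 count or Mycobutin dose is therefore not planned and would be an additional analysis.
- *Variables collected but not listed as factors.* SAP 7.2.2 tabulates body weight, allergy, hemophilia, route of infection and inpatient/outpatient status. None of these is a Section 4.5 factor, so a factor analysis using them would be additional.
- *Multivariable models.* SAP 7.1 specifies none, so a model adjusting one factor for others would be additional.

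**2. Which analyses fall outside it?** The Section 4.5 factor analyses. They are listed in advance, tabulated for every factor (7.2.3.4, 7.2.4.4) and all performed at the final analysis (Section 2). No section makes reporting of a listed factor depend on its result.

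**3. What does the threshold in 3.1 do?** It may be chosen after the p-values are seen, and nothing links it to what is reported. For the listed factors it can change which are highlighted, but it does not remove any from the tables.

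**4. Scale of chance flags (illustration only).** The inputs are:

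- *k* = 15 background factors, by count from the safety part of SAP 4.5: sex, pregnancy, two age groupings, primary disease, race, hepatic dysfunction, hepatitis, renal dysfunction, past history, complications, ophthalmologic complications, HIV-RNA, CD4, CDC class.
- One outcome, any adverse drug reaction. This is the set of tests to which 7.2.3.4 clearly commits.
- Threshold *a*: not given in the SAP, so assumed over 0.01 to 0.20.

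Expected chance flags = *k* × *a*. Chance of at least one, if the tests are independent = 1 − (1 − *a*)^*k*.

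| *a* | Expected flags | Chance of at least one |
|---|---|---|
| 0.01 | 15 × 0.01 = 0.15 | 1 − 0.99^15 = 0.14 |
| 0.05 | 15 × 0.05 = 0.75 | 1 − 0.95^15 = 0.54 |
| 0.10 | 15 × 0.10 = 1.5 | 1 − 0.90^15 = 0.79 |
| 0.20 | 15 × 0.20 = 3.0 | 1 − 0.80^15 = 0.97 |

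These are rough upper guides. The factors overlap (two age groupings, for example), and the exact tests of SAP 7.1.3 are conservative in sparse categories. The table describes the planned tests, to which a threshold might be applied. It does not measure the unplanned analyses, whose number is unknown.

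**The case against.** The strongest reply is that this is a non-confirmatory survey whose plan says so openly. P-values are descriptive, there are no decision rules, and every planned factor is tabulated. Adverse events and adverse drug reactions are tabulated in full by organ class and term, and patients who had them are listed (SAP 7.2.3.1, 7.2.3.2, Section 8). Much of this stands: no safety event and no planned result is withheld. It does not answer the narrow point, because a descriptive label does not tell a reader how many unplanned analyses lie behind the one reported.

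A reader might go further and infer that the planned safety and effectiveness factors are themselves selectively reported, since 3.1 calls the tests exploratory. The documents do not support that. The rule sits in subsections that open with additional analyses and follow the planned subgroup sections, and the listed factors are analysed for every factor. Nor does any text say that the 3.1 threshold decides what is reported.

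A reader might also multiply every listed factor by every outcome: 21 × 3 = 63 safety tests (15 background plus 6 other factors) and 18 × 3 = 54 effectiveness tests. The SAP does not clearly commit to these. The tests in 7.2.3.4 are stated for background factors. The similar analysis for serious reactions and serious events may mean tabulation only. Section 7.2.4.4 names no test, and 7.1.3 makes testing optional. In any case they would be planned analyses, which the rule does not govern.

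**Conclusion.** The concern holds for additional, unplanned analyses only. For these, 7.2.3.5 and 7.2.4.5 write result-dependent reporting into the plan under an undefined criterion. That conclusion rests on the text alone and needs no numerical assumption.

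Its size cannot be computed, because the number of unplanned analyses is unknown. The 0.75 expected chance flags (54% chance of at least one) show only why a flag needs its number of tests beside it. They rest on an assumed 0.05 and, for the percentage, on independence.

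The threshold in 3.1 is a lesser, separate matter: if one is used, readers need to know how it was set. The severity is minor, and the wording is worth correcting because the correction is cheap.

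**What to change.** In SAP 7.2.3.5 and 7.2.4.5, replace the reporting sentence with: *All additional analyses performed will be listed in the report with their results, whatever the result, and marked as unplanned.*

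In SAP 3.1, add: *If a screening threshold is used, its value, when and why it was chosen, and the number of tests it was applied to will be stated beside any flagged factor.*

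A fixed cut-off such as 0.05 need not be imposed. The plan deliberately sets none, and disclosure is enough.

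The cost is two wording changes and a slightly longer report. Data collection and the planned analyses stay as they are.
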